8.3. Statistical methods

8.3.1. Analysis populations

For the efficacy analysis, both an intention-to-treat (ITT) and a per-protocol (PP) approach will be adopted, with the per-protocol analysis being the primary approach, as recommended for non-inferiority studies.

In the PP analysis we will include only subjects who attend all treatment administration visits and that are assessed for infections 4 weeks following every treatment administration. In the ITT population we will include subjects who do not complete all AM administration doses either entirely (missed doses) or inside the pre-specified time window.

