2. STUDY OBJECTIVES

2.1. Primary objective

The primary objective of the **SchistoSAM** (**Schisto**somiasis **S**enegal **A**rtesunate-**M**efloquine) study is to evaluate the efficacy and safety of a single course of artesunate-mefloquine (AM, intervention arm) for the treatment of schistosomiasis in Senegalese primary school-age children, compared to the standard PZQ regimen (control arm).

Endpoint measures:

- Efficacy: Parasitological cure rate (CR, as assessed by microscopy, according to WHO standard) after administration of PZQ and after one AM course (at week 4 – see study flowchart).
- Safety: Frequency and pattern of drug-related adverse events (AEs) and serious AEs (SAEs) up to 4 weeks after PZQ and AM administration.

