8.1. Study hypotheses

The primary hypothesis of this study is that one course of AM is non-inferior in terms of efficacy to the standard PZQ treatment. The secondary hypothesis is that repeated courses of AM are superior in terms of efficacy to the standard PQZ treatment. Furthermore, we hypothesize that novel DNA- and antigen-based diagnostics are more accurate than conventional microscopy in assessing the actual antischistosomal treatment response.

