8.2. Variables of interest

Primary

The primary variables to evaluate are:

- The parasitological cure rates (proportion of subjects negative for both *Schistosoma* species assessed by microscopy over total number in each arm) for AM and PZQ at week 4 after inclusion.
- The patient counts with drug-related adverse events and serious adverse events up to 4 weeks after AM and PZQ administration.

Secondary:

The secondary variables to evaluate are:

- The proportion of cured subjects (CR) of the two different arms at week 10, 16, 24 and 48 (see flowchart).
- The count of patients reporting any form of adverse event up to 4 weeks after each study drug administration.
- The egg reduction rate (ERR) at weeks 4, 10, 16, 24 and 48 (see flowchart). The ERR will be expressed as the percentage of eggs present in each subject at each time point over the number of eggs at baseline.
- The cure rate and egg reduction rate at weeks 4, 10 and 16 after first treatment administration by *Schistosoma* species and by intensity of infection.
- The result of the classic and novel diagnostic tests at baseline and at different time points, as well as a-composite reference standards.
- Clinical and laboratory characteristics related to schistosomiasis-related morbidity at baseline and at weeks 4, 10, 16, 24 and 48
- Prevalence of malaria infection at baseline and at weeks 24 and 48
- The incidence of clinical malaria during the study until week 48
- Counts of cases of anemia both pooled and by severity levels at baseline, week 24 and week
 48
- Binary variables indicating the existence of any or specific types of resistance in the sample size and among the incident malaria cases

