8.3.6 Multiplicity and Missing Data

An interim analysis is planned at week 16 for the efficacy endpoints of cure rate and egg reduction rate after PZQ administration and single and repeated courses of AM. The endpoints of interest will be analyzed and communicated as soon as the data is collected and cleaned. The analysis and results will not influence follow-up or analysis of the rest of the objectives and endpoints in any way.

The primary analysis is a comparison of a single measurement, thus no adjustments for multiplicity are needed.

Subjects who do not attend all treatment administration visits or the follow-up visits will be considered as missing and will be excluded from the per-protocol analysis. No imputation of missing data will be performed.

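### The per-protocol set that decides week-4 non-inferiority excludes children for visits due after week 4, and requires more such visits of the AM arm

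*Protocol*

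**What the plan says.** Protocol section 2.1 sets the primary efficacy endpoint as cure by microscopy "after administration of PZQ and after one AM course (at week 4". Section 8.2 expresses it as a proportion "over total number in each arm) for AM and PZQ at week 4 after inclusion".

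Section 8.3.1 plans an intention-to-treat (ITT) and a PP analysis, "with the per-protocol analysis being the primary approach, as recommended for non-inferiority studies". The PP set will "include only subjects who attend all treatment administration visits and that are assessed for infections 4 weeks following every treatment administration". There is no separate PP definition for week 4.

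Section 8.3.6 gives the exclusion for the PP analysis in different words: "Subjects who do not attend all treatment administration visits or the follow-up visits will be considered as missing and will be excluded". It adds: "No imputation of missing data will be performed".

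Sections 3 and 5.1 give the schedule. AM is taken on three consecutive days at baseline, week 6 and week 12, and the week 6 and 12 visits are for the AM arm only. PZQ is given once. Microscopy is done in both arms at weeks 4, 10 and 16. Sections 4.5 and 6.1 keep children who miss visits or doses in the study.

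Section 8.1 adds a further efficacy claim: "The secondary hypothesis is that repeated courses of AM are superior in terms of efficacy to the standard PQZ treatment".

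**The concern.** A week-4 outcome cannot be changed by what happens at weeks 6 to 16. Excluding a child from the week-4 comparison because of those weeks therefore does nothing to sharpen the estimate of single-course efficacy. It can only discard a valid result or select among valid results.

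The selection differs by arm, because only AM children have dosing visits after week 4. Section 4.5 lists intolerance, repeated vomiting and intercurrent illness before the last dose as reasons for withdrawal, and the later AM courses create those exits in one arm of an open-label trial. If leaving is related to week-4 cure, the AM rate in the PP set is no longer the AM rate after one course. If it is unrelated, the trial loses evaluable AM children for no gain. Either way, the set that carries the non-inferiority decision is not the one the question calls for.

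**Working it through.** **1. The plan's own sample size.** Inputs from sections 4.3 and 8.3.3: cure 75% in both arms, margin 10 points, two-sided 95% interval, 80% power.

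n per arm = (1.960 + 0.842)² × 2 × 0.75 × 0.25 / 0.10² = 294.3, so 295. The plan states 300, which agrees. With the Wilson-score (Newcombe) interval for a difference, 300 per arm gives about 81% power. The 363 recruited per arm, less the planned 20% loss, leaves 290 (363 × 0.80 = 290.4) and 79.8% power.

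**2. Contacts needed to enter the PP set under section 8.3.1.**

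| | AM | PZQ |
|---|---|---|
| Dosing visits | 3 courses × 3 days = 9 | 1 |
| Assessments 4 weeks after treatment | 3 (weeks 4, 10, 16) | 1 (week 4) |
| Total | 12 | 2 |
| Of these, after week 4 | 6 dosing + 2 assessments = 8 | 0 |

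**3. The same count under a broad reading of section 8.3.6.** If its follow-up visits mean all scheduled parasitology to week 16, a PZQ child must also attend weeks 10 and 16. The count after week 4 becomes 8 for AM and 2 for PZQ. The remaining difference is the six dosing days at weeks 6 and 12. If weeks 24 and 48 count as well, both arms gain two more.

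**4. How many AM children this could remove.** The protocol gives no visit-level attendance, so the following is assumed. With independent attendance s at each of the 8 later contacts, the share of AM children assessed at week 4 who stay is s⁸: 92%, 85%, 78% and 66% for s = 99%, 98%, 97% and 95%. Counting each 3-day course as one occasion leaves 4 later occasions, and s⁴ is 96%, 92%, 89% and 81%. A 15% loss thus corresponds to s = 98% on the first count, or about 96% on the second (0.96⁴ = 0.849).

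**5. Effect on the decision.** Assume 290 per arm assessed at week 4, 15% of AM then dropped (290 × 0.85 = 246.5, taken as 246) and all PZQ kept. If the dropped children's week-4 cure rate is d points below that of those kept, the AM rate in the PP set exceeds the full AM rate by 0.15 × d. So d = 10 gives +1.5 points, d = 20 gives +3.0 and d = −10 gives −1.5. Exact binomial enumeration of the chance that the lower limit exceeds −10 points gives:

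- No shift: false non-inferiority (true 65% vs 75%) 2.6%; power at 75% vs 75% falls from 79.8% to 75.7%.
- Shift +1.5 points: false non-inferiority 5.8%.
- Shift +3.0 points: false non-inferiority 11.8%.
- Shift −1.5 points: false non-inferiority 1.0%; power at true equality 61%.

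**6. Cross-check with a different model.** Take 300 per arm assessed at week 4 and let AM retention depend on week-4 status. With 90% of cured and 85% of uncured kept, the AM rate becomes 0.65 × 0.90 / (0.65 × 0.90 + 0.35 × 0.85) = 66.3%, and simulated false non-inferiority is 5.3%. With 90% and 80% kept it is 10.3%. Reversed, with 80% and 90% kept, it is 0.4%, and power at true equality is 53.4%.

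**The case against.** **ITT is run as well, and children stay in the study.** This stands as mitigation. The week-4 results are not lost to the trial, and a gap between PP and ITT would be visible. But section 8.3.1 names PP as primary and gives ITT no stated part in the decision.

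**A reader might infer that PZQ children face no attendance test after week 4.** That holds under section 8.3.1 only. Section 8.3.6 can be read as dropping PZQ children for missed later follow-up, so the documents do not support the flat statement. They support a conflict between two sections, with the week 6 and 12 dosing visits required of AM alone on either reading.

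**A reader might infer that the rule favours AM.** The protocol does not show this. Nothing in it says that children who miss later visits were less often cured at week 4. Section 3 masks parasitology results to the clinical teams, which weakens selection on known response. Selection through tolerance remains possible, but its sign is open.

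**The inputs are chosen.** This also stands. Neither the 15% nor the 10- and 20-point differences come from the protocol. Dosing is directly observed, section 6.1 allows some delay and section 4.5 promises active follow-up, so later attendance may be high. If the planned 20% loss already covers these exclusions, the AM set is not reduced below 290 and the plan's power is not eroded. The selection question would remain.

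**A reader might also conclude that non-inferiority must be shown in both ITT and PP.** That is a preference about the decision rule. A correctly defined week-4 PP set removes this defect without it.

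**Conclusion.** The point holds as a defect in a rule that the protocol itself fixes. The only PP set defined, which is primary for the week-4 decision, conditions on attendance after the endpoint, and does so unequally by arm. Sections 8.3.1 and 8.3.6 also disagree on who is excluded. These conclusions rest on the text alone.

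The size is conditional. In the scenario of 15% AM loss after week 4, false non-inferiority runs from 1.0% to 11.8% for shifts of −1.5 to +3.0 points, against 2.6% with no shift. Power falls by about 4 points with no shift and to 61% with a shift of −1.5. With near-complete later attendance the effect would be small.

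There is a secondary point on the superiority claim for repeated AM. Section 8.3.1 makes PP primary for efficacy in general, but the reason it gives applies only to non-inferiority, and section 8.3.4 names no set. No size is given here. A child who misses week 16 has no week-16 result, so the week-4 figures cannot be carried over.

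**What to change.** In section 8.3.1, define a week-4 PP set by events up to week 4 only, in the same way for both arms: all doses of the randomised first treatment (first AM course or single PZQ dose) received in the protocol's window, and a week-4 microscopy result. Keep the all-courses PP set for the week 10 and 16 analyses only.

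Reword section 8.3.6 to match, saying which follow-up visits count for which time point.

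As a secondary change, state that ITT is the primary set for the superiority hypothesis on repeated AM, with PP supportive.

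The cost is a few sentences in the protocol, carried into the SAP. It needs no new data, visits or children, and clinical management is untouched. It should be settled before the week-16 interim analysis described in section 8.3.6, since that analysis already reports cure rates.

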3. STUDY DESIGN

The **SchistoSAM** study is an open label, two-arm, individually-randomized controlled trial among infected primary school-age children in northern Senegal, with a non-inferiority design.

The study will take place during the rainy season (July-October) to maximize the potential benefits of repeated AM administrations on both schistosomiasis and malaria.

At baseline, prior to the first drug administration, all children fulfilling the study criteria (chapter 4.2) will undergo a full parasitological and morbidity assessment of:

- schistosomiasis infection: by microscopy (stool Kato-Katz and urine filtration) and point-of-care assays on site (POC-CCA) as well as additional diagnostics on preserved urine/stool samples (a UCP-LF CAA assay and a real time stool and urine PCR)
- 2. schistosomiasis systemic and organ-specific morbidity: by clinical evaluation, ultrasound, point-ofcare morbidity markers and hemoglobin level
- 3. malaria infection: by determination of prevalence through molecular testing on preserved blood samples, and prevalence/pattern of molecular markers of resistance
- 4. malaria morbidity: by measurement of proportion and severity of anemia

Subsequently, children will be randomized and assigned to one of the two following study arms:

- 5. **AM arm**: Three-day course of AM (A: 4 mg/kg and M: 8 mg/kg per day, given once a day for three days) administered at baseline and repeated twice at 6-week intervals (intervention).
- 6. **PZQ arm**: Single dose of PZQ (40 mg/kg) administered at study inclusion (control arm/standard of care).

The 6-weeks interval between AM administrations corresponds to the time lapse for larval maturation (from infection to adult worms). In addition, this 6-week period should minimize/prevent the risk of cumulative mefloquine-associated toxicity.

[figure not shown]
Parasitological assessments of schistosomiasis (urine and stool microscopy and POC-CAA) will take place in both arms at week 4, 10 and 16 after first administration of AM or PZQ. Full parasitological assessment of schistosomiasis and malaria (urine, stool and blood analysis) will be repeated at week 24 and 48 post-inclusion.

Morbidity assessment will be repeated as described here above at week 24 and 48 after initial treatment. These assessments are described in more detail in chapter 5.

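### The per-protocol set that decides the week-4 non-inferiority test depends on attendance up to week 16 in the AM arm only, so events after the endpoint can affect the primary comparison

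*Protocol*

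**What the plan says.** Protocol sections 2.1 and 8.2 place the primary efficacy endpoint, parasitological cure by microscopy, at week 4, after PZQ or one AM course. Section 8.3.1 plans both ITT and PP analyses, "with the per-protocol analysis being the primary approach, as recommended for non-inferiority studies". It gives a single PP definition for all efficacy analyses. The set will "include only subjects who attend all treatment administration visits and that are assessed for infections 4 weeks following every treatment administration".

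Section 3 gives AM as three courses six weeks apart and PZQ as one dose at inclusion. Section 5.1 places the assessments after the second and third courses at weeks 10 and 16.

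Section 8.3.6 words the exclusion in another way: "Subjects who do not attend all treatment administration visits or the follow-up visits will be considered as missing", and such children leave the PP analysis. It does not say which follow-up visits are meant. Nothing is imputed. The same section states: "An interim analysis is planned at week 16 for the efficacy endpoints of cure rate and egg reduction rate". Those results are to be communicated once the data are clean, while the visits at weeks 24 and 48 are still to come.

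**The concern.** A week-4 question should be answered in children selected on what was known by week 4. Here membership of the deciding set depends on behaviour after the outcome has been measured, and the condition falls on one arm. Under 8.3.1 an AM child must attend courses 2 and 3 and be assessed at weeks 10 and 16. A PZQ child has nothing further to fulfil after week 4.

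The routes out of the set are also uneven. Section 4.5 lists reasons for withdrawal that apply before the last dose of study medication, such as severe gastric intolerance, psychiatric illness, a vomited repeat dose or new chronic medication. Between week 4 and week 48 only AM children have study doses due. For withdrawn children, section 4.5 promises efforts for at least the week 24 and 48 visits, so the week 10 and 16 assessments that 8.3.1 requires are not assured.

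At stake is the non-inferiority decision itself. Valid week-4 results in the AM arm leave the primary analysis, and if the children who leave differ in week-4 cure from those who stay, the AM cure rate is shifted.

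**Working it through.** **Inputs from the protocol.** Margin 10 points and two-sided 95% CI by Wilson's score method (8.3.3); PZQ cure 75%, AM limit 65%, 80% power, 300 required and 363 recruited per arm (4.3). For the difference I use Newcombe's interval built from Wilson limits, with lower limit

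L = (pA − pP) − √[(pA − lA)² + (uP − pP)²],

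where lA is the lower Wilson limit for AM and uP the upper Wilson limit for PZQ. Non-inferiority is declared if L > −0.10. Probabilities are exact sums over both binomial distributions.

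**1. The plan's own figure.** With both arms at 75%: n = (1.960 + 0.842)² × 2 × 0.75 × 0.25 / 0.10² ≈ 295 per arm, close to the stated 300. Exact power at 300 per arm is 81.1%. The chance of declaring non-inferiority at 65% v 75% is 2.6%.

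**2. Attendance needed under 8.3.1.** AM: 9 dosing days + 3 assessments = 12. PZQ: 1 + 1 = 2. A set limited to week 4 would need 3 + 1 = 4 in AM.

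**3. Later loss in AM.** Assumptions, since the protocol gives no figures: 300 per arm evaluable at week 4; a share e = 10-15% of AM lost to the PP set afterwards; week-4 cure in the lost children differs by g from the rest. Then n(AM) = 300(1 − e), i.e. 270 or 255. Cure among those kept is p + e·g if the lost children do worse and p − e·g if they do better, where p is the true AM rate. PZQ stays at 300 and 75%.

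| Link to week-4 cure | Kept AM cure, e = 10% / 15% | Result |
|---|---|---|
| None, p = 75% | 75% / 75% | power 78% / 77% |
| Lost 5 points lower, p = 65% | 65.5% / 65.75% | false non-inferiority 3.4% / 3.9% |
| Lost 15 points lower, p = 65% | 66.5% / 67.25% | false non-inferiority 6.0% / 8.6% |
| Lost 5 points higher, p = 75% | 74.5% / 74.25% | power 74% / 70% |
| Lost 15 points higher, p = 75% | 73.5% / 72.75% | power 64% / 54% |

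With no link, error at the margin stays at about 2.5%. The power figures in the last two rows combine the shift with the smaller AM sample; the first row shows the sample-size part alone.

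**4. How few children matter near the limit.** Take PZQ 225/300 cured.
- AM 214/300 gives L = −10.7% (not shown). Remove three uncured AM children for later absence: 214/297 gives L = −9.99% (shown).
- AM 217/300 gives L = −9.7% (shown). Remove four cured AM children: 213/296 gives L = −10.09% (not shown).

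**5. Precision alone, from 363 per arm (assumed miss rates).**
- Each attendance missed independently 2% of the time: AM 363 × 0.98¹² = 285, PZQ 363 × 0.98² = 349, power 82.3%. With a week-4 AM set (363 × 0.98⁴ = 335), power is 85.7%.
- At 3%: AM 252, PZQ 342, power 78.6%. With a week-4 set (321), 84.5%.
- If misses cluster, with one 3% chance per course and per assessment: AM 363 × 0.97⁶ = 302, PZQ 342, power 83.2%.

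**The case against.** **Bias is not shown.** This stands. If later absence is unrelated to week-4 cure, only precision is lost. The protocol also weakens any link: parasitology results are masked to the clinical teams (section 3) and participants are actively followed up for all visits (4.5). A reader might infer that later events will change the primary result. The documents support only that they can.

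**Sections 8.3.1 and 8.3.6 may agree.** In 8.3.6 the word for all attaches to the treatment visits, and the follow-up visits could simply be the assessments four weeks after each administration. A reader might infer a second rule that certainly reaches weeks 24 and 48, so that the result reported at week 16 would be revised. The text does not establish that. It leaves the visits unnamed, and the consequence follows only on the wider reading.

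**The size rests on chosen inputs.** This also stands. The dropout share, the cure gap and the miss rates are assumptions. Power falls below 80% on attendance alone only in the independent 3% case, which implies 31% AM loss, against the 20% allowed in section 4.3. Section 6.1 lets the three doses be given within 5 days, so clustered misses are more plausible than independent ones.

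**ITT is planned.** It keeps these children, and data collected before withdrawal are retained for analysis (4.5), so the week-4 outcomes are lost to the PP analysis only. But PP is the primary approach. It does not follow that ITT must also succeed before non-inferiority is claimed; that is a separate design choice which this defect does not require.

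**The SAP could define a week-4 set.** Section 8 makes the SAP binding. But the protocol does not leave the set open: it states a rule, and a week-4 set in the SAP would depart from it unless 8.3.1 is corrected.

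**Conclusion.** The point holds as stated in the heading. The only PP definition in the protocol makes the primary week-4 comparison conditional on AM attendance and assessment up to week 16, with no matching condition in the PZQ arm. The certain effect is fewer AM children in the deciding analysis whenever later visits are missed. The possible effect is bias in either direction.

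With 10-15% later AM loss (assumed), the precision cost is small: power 78-77% instead of 81%. With a modest 5-point gap, false non-inferiority is 3.4-3.9% instead of 2.6%, or power is 74-70%. With a 15-point gap the figures are 6.0-8.6% and 64-54%. A result close to the margin can turn on three or four children. The wording of 8.3.6 is an ambiguity: if weeks 24 and 48 are meant, the set is not final when the week-16 analysis is reported.

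**What to change.** In 8.3.1, define PP sets by endpoint. For the week-4 test, use the same rule in both arms: the first AM course or the PZQ dose received as specified, plus week-4 microscopy, regardless of later visits. Keep the conditions for weeks 6 to 16 for the repeated-course analyses only. In 8.3.6, limit the follow-up visits to the week-4 assessment for the primary set, so that both sections give one rule and the set is fixed before the week-16 analysis. Naming the treatment visits would also help, since Table 1 lists a further PZQ dose for both arms at week 48.

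The cost is protocol wording, carried into the SAP. No visit, sample size or data collection changes, and AM children with valid week-4 results return to the primary analysis.
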